7.2.1 Short-form McGill Pain Questionnaire (SF-MPQ)

The SF-MPQ consists of a 15 item pain rating index. The severity of each item will be scored as None (0), Mild (1), Moderate (2), or Severe (3). The total SF-MPQ score is the sum of the severity scores for each item. The total score can range from 0 to 45. During the double-blind treatment period, the SF-MPQ will be collected on Days 84, 98, 112, and 119.

7.2.2 Time to Rescue after Randomization

If at any time a subject experiences intolerable pain, the subject will be allowed to rescue. The day, time and amount of rescue medication provided to address the intolerable pain will be recorded. Rescue may include providing oral or intravenous medication, as well as increasing the pump speed to titrate the subject back to an effective dose of intrathecal hydromorphone.

The number of days to rescue will be calculated by calculating the number of hours between the time of randomization and the time of rescue. The number of hours will then be divided by 24 to obtain the number of days.

7.2.3 Oral Opioid Supplement Consumption

The total number of milligrams consumed of any oral opioid product from Day 84 through the end of study will be calculated for each subject. Opioid consumption was to be recorded via subject diaries throughout the study. As a rule, subject diaries are not queried for data clarification purposes. Occasionally, a subject would report opioid consumption that was not recorded on the subject diary. This data was then recorded on the concomitant medication CRF page by the study site staff. In order to calculate the total opioid consumption during the randomized phase of the trial, both CRF modules will be utilized. Medications recorded as concomitant medications, with ATC3 text equal to "OPIOIDS" and with a start date on or after the randomization date will be combined with records from the Opioid Products Administered CRF.

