Prior to rescue medication being administered, subjects will complete Day 119 study assessments, if possible. After confirming with the investigator that it is acceptable to take rescue medication, if a subject cannot return to the study site for assessments they will be instructed to complete a VASPI score on the remote monitoring device immediately prior to taking oral rescue medication. If the subject can return to the site, rescue may be performed by either oral or IV medication being administered or by increasing the pump speed to achieve a therapeutic dose of hydromorphone hydrochloride, or both.

Subjects who are treatment failures or those who are dropped from the study prior to randomization under this protocol will be permitted to enroll into Mallinckrodt clinical study CNS-HYD202US if the PI believes that the subject meets the study selection criteria and would benefit from participation in the study. For any subject continuing therapy on the CNS-HYD202US trial, the Day 119 (or failure visit) assessments will be considered the last day on the CNS-HYD201US trial and the first day of CNS-HYD202US. Subjects in the CNS-HYD201US trial who were dropped prior to randomization and judged by the primary physician to benefit from participation in CNS-HYD202US will complete the study visit that they are on, go directly into CNS-HYD202US and complete scales there at the Screening and Baseline Visit. Subsequent visits, including re-titration onto hydromorphone hydrochloride if necessary, will be considered part of the CNS-HYD202 US trial.

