#### 9.7 Final Visit

Subjects who do not enter the CNS-HYD202US long-term safety trial will return to the investigational site for the final visit 2 weeks ( $\pm$  4 days) after discontinuation from the trial. At the final study visit subjects will be assessed for AEs and clinical signs or symptoms of an inflammatory granuloma as well as other procedures according to Appendix A, Table A- 2. Also during the final visit the investigator will remove all study drug from the subjects pump and will continue the subjects normal standard of care.

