PGIC ^j		Х		Х		Х	Х	

Table 2: Schedule of Study Procedures: Final 7 Days of Continuous Dosing, Randomized Withdrawal and Efficacy Evaluation Period

a. Study day is based on Day 1 defined as the first day at a therapeutic dose of intrathecal hydromorphone., There is no Day 0 in this trial.

b. All visit days are +/- 1 day after Day 77 except for the final study visit.

c. On Days 84, 91, 98, 105 and 112 all subjects will have a pump adjustment. For those subjects randomized to maintain therapy, the adjustments will be a mock change to the dose, but no change will actually be made. For control group subjects randomized to be weaned off medication, the pump will be adjusted to give a 75%, 50%, 25%, 12.5% and 0% dose on each successive dose adjustment visit.

d. For the 0% dose, the pump will be set to the shipping mode (minimal speed possible)

e. On Day 119, or after treatment failure, all subject will receive scheduled Day 119 assessments before rescue medication is administered, if possible. If the subject cannot come to the site prior to rescue, they will be instructed to take a final VASPI using the remote monitoring device prior to taking oral rescue medication. After completion of the randomization period or rescue due to intolerable pain, subjects may be eligible to enter the CNS-HYD202US long term safety trial for an additional 12-months of hydromorphone therapy.

f. Subjects that discontinue or do not enter the CNS-HYD202US trial will return to the site 2 weeks after their last visit to have a final study visit. This visit can be +/- 4 days of the target date.

g. Oral opioid up to a maximum of 60 mg morphine-equivalence of oral opioid per day is allowed after Day 84 only for the purpose of managing withdrawal symptoms experienced as subjects are weaned off intrathecal medication. Doses of opioids in excess of 60 mg morphine-equivalence oral opioid per day, or other interventions to manage pain will be considered a treatment failure.

h. If there are clinical signs of an inflammatory granuloma as defined in Section3.3 (of the protocol), the Medical Monitor should be notified and an MRI or CT myelogram scheduled to confirm the pathology of the granuloma.

i. VASPI assessments are performed twice daily by the subject using a remote monitoring device that can capture VASPI measurements at approximately the same times each day.

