7.1 Primary Efficacy Endpoint

The primary efficacy endpoint is the proportion of subjects who are treatment failures during the double-blind randomized withdrawal period. After randomization, a treatment failure will be defined by the following criteria:

- 1. Any subject who experiences an increase of 20 mm or more above the baseline value on a 100 mm VASPI based on the average of 5 days, or
- 2. Any subject who experiences intolerable pain that in the opinion of the investigator requires intervention (i.e. rescue), or
- 3. Any subject who has other interventions for pain that violate the protocol from Day 84 to 119 that includes:
 - a. Requires oral opioid supplement in excess of 60 mg/day morphine-equivalent to manage withdrawal symptoms, or
 - b. Has a change in non-opioid oral prescription medications or nonpharmacological treatments being administered for the management of pain.

Note: A subject who does not have sufficient data for evaluation, drops out for any other reasons that are not listed above or who experiences withdrawal syndrome as identified by COWS > 12 during the double-blind treatment phase will **not** be classified as a treatment failure in the primary efficacy analysis.

VASPI Calculation Algorithm

VASPI scores will routinely be collected twice each day. The daily VASPI score from Day 77 to 119 will be computed as follows:

- As the average of the two scores when both of the twice-daily VASPI measures are present.
- If only one score is present, then the daily score will be equal to that non-missing value.

• If both scores are missing, then the daily score will be missing.

The 5-day baseline (Days 77-83) average VASPI will be computed as follows:

- If the daily score is present on days 79, 80, 81, 82, and 83, then the 5-day average is the average of days 79-83.
- If one of the daily scores from days 79-83 is missing, then the day 78 value (if present) will be included in the 5 daily scores to be averaged. If the day 78 value is also missing, then the day 77 value will instead be used.
- If two of the daily scores from days 79-83 are missing, then the day 78 and day 77 values (if present) will be included in the 5 daily scores to be averaged.

During the double-blind randomized withdrawal period, the 5-day average will be calculated as follows:

- If the daily score is present on all 5 consecutive days, then the 5-day average will be calculated using the data from these days.

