8.6 Comments on Statistical Analysis

The following general comments apply to all statistical analyses and data presentations:

Summaries will include frequency and percentages for categorical data and frequency, mean, standard deviation, median, minimum, and maximum for quantitative data.

- Where appropriate and unless otherwise specified, analyses will be presented by randomized treatment arm: hydromorphone arm or titrated down (control) arm.
- Duration variables will be calculated using the general formula: Duration = (end date start date) + 1.
- Individual subject listings of all data represented on the eCRFs will be provided to facilitate the investigation of tabulated values and to allow for the clinical review of all data.
- Version 9.1 or greater of SAS statistical software package will be used to provide all summaries, listings, and graphs described in this document.
- All raw data will be presented to the original number of data places. The means and medians will be presented to one more decimal place than the raw data. The standard deviations will be presented to two more decimal places than the raw data. For averages of averages, the means and medians will also be presented to one more decimal place than the raw data and the standard deviations will also be presented to two more decimal places than the raw data.
- Generally, the denominator for percentages will be based on the number of subjects in the study population. However, for cases where appropriate, the denominator for percentages will be based on the number of subjects with non-missing data appropriate for summary purposes. Unless otherwise noted, all percentages will be presented to one decimal place.
- There are approximately 10-30 study sites in this study. Due to the large number of study sites and the small numbers of subjects per site, the analysis of efficacy endpoints will not include adjustments for study site. However, descriptive summaries of the primary endpoint will be provided by site.

• Analyses for the randomization phase, Day 84 through Day 119, will be calculated for the period defined as randomization date through end of study date, as study day of randomization and Day 119 visit may not always occur on the scheduled study days (84 and 119) due to various circumstances.

9 Statistical Analyses

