9.5.2 Secondary Efficacy Analyses

Safety is the most important secondary endpoint. Other secondary endpoints include quality of life / pain scale assessments.

For the purpose of efficacy analyses, 'baseline' will be Day 84.

The change from baseline) to Day 119 in the BPI (pain severity 'worst', pain severity 'average', calculated mean pain severity, and calculated mean pain interference with function.) will be analyzed using an ANCOVA model with treatment group as a factor and the baseline BPI as a covariate. The change from baseline to Day 119 in the SF-MPQ and in oral opioid supplement consumption will also be analyzed using this same type of ANCOVA model.

The distributions of time to rescue will be summarized in each treatment group using the Kaplan- Meier method. Subjects who do not receive rescue medication will be censored at their date of last follow-up. The two groups will be compared using the log rank test.

The PGIC on Day 119 (or at the time of rescue) will be analyzed using the Cochran-Mantel-Haenszel mean score test (using equally spaced scores).

All secondary analyses will be carried out using two-sided tests at the 5% level of significance.

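### Oral opioid consumption is a raw-milligram total over unequal time on study, tested as change from a baseline the SAP does not define, so it can misstate the arm difference in daily use

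*SAP*

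**What the plan says.** SAP 7.2.3 takes, for each subject, "The total number of milligrams consumed of any oral opioid product from Day 84 through the end of study". The sources are the opioid CRF fed by subject diaries, plus concomitant-medication records classed as opioids that start on or after the randomization date. No conversion factor and no per-day scaling is given.

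SAP 8.6 says that randomization-phase analyses "will be calculated for the period defined as randomization date through end of study date", because the visits do not always fall on the scheduled days. When that date falls depends on the subject:

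- For anyone continuing into the extension, Protocol 3.1 says "the Day 119 (or failure visit) assessments will be considered the last day on the CNS-HYD201US trial".
- Protocol 9.7 says "Subjects who do not enter the CNS-HYD202US long-term safety trial will return to the investigational site for the final visit 2 weeks" after discontinuation. SAP Table 2, footnote f, likewise has subjects who "do not enter the CNS-HYD202US trial will return to the site 2 weeks after their last visit".

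For the analysis, SAP 9.5.2 states "For the purpose of efficacy analyses, 'baseline' will be Day 84" and then "The change from baseline to Day 119 in the SF-MPQ and in oral opioid supplement consumption will also be analyzed" by ANCOVA, with treatment as factor and the baseline value as covariate. SAP 8.5 exempts this endpoint from last-observation-carried-forward.

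The trial's own opioid limits are on a different scale. Failure criterion 3a in SAP 7.1 reads "Requires oral opioid supplement in excess of 60 mg/day morphine-equivalent to manage withdrawal symptoms", and the allowances in the Protocol Synopsis and SAP 4 are also in morphine-equivalents.

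**The concern.** Three features of the definition stop the number from measuring what a reader would take it to measure.

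- **Unit.** Milligrams of agents of different potency are added as if equal, so the total depends on which opioid was prescribed.
- **Time.** The total grows with days on study. Failure can end those days, and failure is what the treatment is expected to change.
- **Baseline.** The planned model needs a Day 84 consumption value. A total that starts on Day 84 has none, and the SAP defines no earlier one.

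What is at stake is the interpretation of one listed secondary efficacy endpoint. After randomization, oral opioid is meant only for withdrawal symptoms (Protocol 3.5.1.3), and only the control arm is tapered, so control may truly use more per day. Shorter control follow-up would shrink that excess in the total.

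**Working it through.** **Inputs.** Failure is 20% on active and 55% on control, with 40 per arm (SAP 8.1). The double-blind period is 119 − 84 = 35 days. The documents give no distribution of exit times, so the exit day of failures is an assumption, varied from day 7 to day 28 after randomization.

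**The plan's own figure.** The documents give no figure for this endpoint. The failure rates do reproduce the stated power of more than 90% for the primary endpoint. Pooled p = 0.375; null SE = √(2 × 0.375 × 0.625/40) = 0.1083; alternative SE = √(0.20 × 0.80/40 + 0.55 × 0.45/40) = 0.1009. Then (0.35 − 1.96 × 0.1083)/0.1009 = 1.366, which is 91.4% power.

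**Time on study.** Suppose daily use is equal and constant and every failure leaves at the failure visit. The ratio of totals is then the ratio of mean days, where mean days = (1 − f) × 35 + f × e, f is the failure rate and e the exit day.

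| Exit day e | Active days | Control days | Control/active | Daily excess hidden |
|---|---|---|---|---|
| 7 | 0.80×35 + 0.20×7 = 29.4 | 0.45×35 + 0.55×7 = 19.6 | 0.67 | 50% |
| 14 | 30.8 | 23.45 | 0.76 | 31% |
| 17.5 | 31.5 | 25.375 | 0.81 | 24% |
| 21 | 32.2 | 27.3 | 0.85 | 18% |
| 28 | 33.6 | 31.15 | 0.93 | 8% |

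The last column is active days/control days − 1: the true control excess in daily use that would appear as equal totals. Counting days inclusively, as the SAP 8.6 duration formula does (36 days; mean 18.5 for failures spread evenly), gives 32.5 vs 26.375 days, again 19% lower.

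**What moves this.**

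- Failures who stay on study reduce it. A subject who fails on the 5-day pain average counts as a failure whether or not rescue is given (Protocol 3.5.1.3), and no section found sets an exit date for that subject. If half of failures stayed to Day 119 (an assumption), their mean would be (17.5 + 35)/2 = 26.25 days. That gives 33.25 vs 30.19 days, 9% lower.
- Rescue opioid inside the window raises the total of subjects who are rescued, and more of those are expected on control.
- A large true excess survives. An assumed fivefold control excess per day would show as 5 × 0.81, about fourfold.

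**Unit.** Protocol 1.2.1 gives a parenteral ratio of 1.5 mg hydromorphone to 10 mg morphine, and no direct oral ratio between the two drugs. For illustration only, 60 mg morphine-equivalent counts as 60 mg if taken as morphine and as 60 × 1.5/10 = 9 mg if taken as hydromorphone. For an assumed ratio of 1:4 to 1:8 it counts as 15 to 7.5 mg. Nothing in the documents suggests that the choice of agent differs by arm.

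**Baseline.** If baseline is set to 0 for everyone, change equals the total and the covariate is constant, so the ANCOVA reduces to a two-group comparison of totals. If a single day's diary amount were used, a one-day quantity would be subtracted from a multi-week sum. The SAP chooses neither.

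**The case against.** The strongest reply has four parts.

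*Equal constant daily use is not what the design expects.* This stands. Subjects are meant to be off oral opioid just before randomization (Protocol 9.4), so active use should be low and a large control excess would remain visible. The 19% is an illustration of the mechanism, not an expected bias.

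*The window is not as loose as it looks.* This largely stands. A reader might infer from the final-visit sentences that two extra weeks of use are counted for subjects who do not roll over. SAP 8.6 speaks of Day 84 through Day 119, and the oral-opioid row of SAP Table 2 stops at Day 119, so that is an unlikely reading. Early exit at a failure visit remains.

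*Baseline use may be on file.* This stands. A reader might infer that no baseline can exist, but SAP 7.2.3 says diaries were kept throughout the study. The value is undefined, not shown to be unavailable. The analysis still cannot be run without a choice that the SAP does not make.

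*The data are already unblinded, so the planned test should not be replaced.* This stands as a limit on the remedy. Leaving the text alone is no safer, because someone must choose a baseline after unblinding in any case.

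**Conclusion.** As written, the endpoint can misstate the arm difference in daily oral opioid use, and its ANCOVA lacks a defined baseline. With every failure leaving at the failure visit and equal constant use, the control total is about 19% lower for mid-period exit, and about 7% to 33% lower for exit at day 28 to day 7. This rests on the planned failure rates and on assumed exit times, and it covers only those scenarios.

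A reader might infer that the analysis is biased in a known direction, against finding a control excess. The documents do not support that: failures who stay on study shrink the gap and rescue opioid works the other way. Nor do they show an arm imbalance from mixed units, which mainly add noise. The primary endpoint and its power are unaffected. The correction is worth making because it is cheap and because the analysis cannot be programmed from the present text without an undocumented decision.

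**What to change.** In SAP 7.2.3 and 9.5.2 (Tables 14.2.3.1.3 and 14.2.3.1.4):

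- (a) Convert each oral opioid record to morphine-equivalent milligrams with one fixed table. Count and list records that cannot be converted, since SAP 2 permits no further efficacy cleaning.
- (b) State that the window runs from randomization to the earliest of the failure or rescue date, discontinuation and the Day 119 visit. Where there is no failure visit, use the date a failure criterion is first met.
- (c) Add mean morphine-equivalent milligrams per day in that window, compared between arms with treatment as factor. Use no change score or covariate unless a pre-randomization diary value is defined. Before that is done, the Protocol Synopsis and SAP 4, which allow some oral opioid from Day 77, must be reconciled with Protocol 9.4, which has subjects off it on Days 77 to 83.
- (d) Show results with and without opioid taken at or after the recorded rescue time (SAP 7.2.2), since excluding it changes what is estimated.
- (e) Report the planned total and its between-arm comparison alongside. Date the change in SAP Section 10 and label it in the CSR as made after unblinding.

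The cost is SAP wording, one conversion table and reprogramming of two tables on the locked data. The downside is a small post-unblinding addition. A per-day mean over windows ended by failure also does not fully remove time-varying use during the taper, and it may understate control use in early failures.

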#### 3.6 Concomitant Medications

#### 3.6.1 Prior and Concomitant Medications

Prior medications are defined as medications that were taken within 30 days prior to initial dosing with study drug.

Concomitant medications are defined as medications taken any time after the start of dosing until the final visit. For concomitant medications being taken during the dosing period with intrathecal hydromorphone hydrochloride and the randomized withdraw, if the medication is needed long term the medication should be recorded as a concomitant medication and maintained at a constant dose during the trial.

There is inadequate systematic experience with the use of intrathecal hydromorphone hydrochloride in combination with other medications to predict specific drug-drug interactions. Interactions attributed to the combined use of intrathecal hydromorphone hydrochloride and other epidural drugs include hypotension and respiratory depression.

01 August 2016 40 CONFIDENTIAL

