Subjects may be given oral supplemental medication for pain up to a maximum of 180 mgequivalent morphine per day prior to Day 77 of treatment, however, the objective of the trial during this period is to achieve an optimal dose of intrathecal hydromorphone hydrochloride and reduce or eliminate any oral supplement. Oral supplement in excess of 180 mgequivalent morphine per day or other interventions due to intolerable pain, is not permitted and the subject will be withdrawn from the trial and weaned off intrathecal hydromorphone hydrochloride and converted to other appropriate pain therapies. From Day 77 to Day 119 or day of rescue, subjects are permitted up to 60 mg-equivalent morphine per day only to manage possible withdrawal symptoms.

On Day 77 the pump should be refilled with intrathecal hydromorphone and any final adjustments made to the daily dose or programming. On Day 77, the subject will be given a remote monitoring device to measure VASPI scores twice daily in the morning (5:30 am to 12:00 noon) and in the evening (6:00 pm to 11:45 pm). After Day 77 and during the randomized double-blind period there should be no dose adjustments to intrathecal hydromorphone hydrochloride other than those dictated by the protocol for subjects on the control arm who have their dose titrated downward. After Day 77, there should also be no changes to the pump programming for simple continuous, complex continuous or PTM dosing regimens until after the completion of the trial.

At the end of the 12 week continuous dosing period, subjects who meet criteria for randomization will be randomized in a 1:1 ratio to either remain at their current dose of hydromorphone or who have their dose titrated downward (control group) in a blinded fashion. The criteria for randomization is defined as an average VASPI score of 50 mm or less on a scale of 100 mm for the last 5 days with daily pain measurements prior to randomization on Day 84. After Day 77 the subject should be weaned off any oral supplement of opioid or other prescription medications prior to randomization. For those subjects randomized to be withdrawn from hydromorphone therapy on Day 84, the pump speed will be adjusted to decrease the total daily dose each 7 days (\pm 1 day), starting at a dose

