9.2.2 Medications

Prior medications are defined as medications that were taken within 30 days prior to initial dosing with study drug. Concomitant medications are defined as medications taken any time after the start of dosing until the final visit. Medications are also considered concomitant if their stop date is unknown or marked as continuing. Medications will with missing start dates will be considered ongoing on the first day of study drug administration except where positive confirmation is available that the medication was stopped before study drug administration.

The World Health Organization Drug Dictionary (WHO-DD) will be used to classify prior and concomitant medications by therapeutic class and preferred term. The WHO-DD version will be noted in the CSR. The number and percentage of subjects receiving concomitant medications will be summarized by Anatomical Therapeutic Chemical (ATC) level 3, preferred term, and treatment arm. Subjects will be counted only once for an ATC class and preferred term, even if the subject took the same medication on multiple occasions. Prior medications will be summarized in a similar manner.

A listing of medications will be prepared.

9.2.1 12-Lead Electrocardiogram (ECG)

A safety ECG will be performed at screening to assess any cardiovascular abnormalities for the purpose of determining eligibility for this trial. The number and percentage of subjects with normal, abnormal not clinically significant and abnormal clinically significant ECGs at Screening and Baseline will be summarized.

ECG results will also be listed.

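### The concomitant-medication part of the oral-opioid endpoint (SAP 7.2.3) selects records by start date and drug class only, so it can omit oral intake that the endpoint covers and admit intravenous opioid that it does not

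*SAP*

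**What the plan says.** SAP 7.2.3 gives the endpoint as "The total number of milligrams consumed of any oral opioid product from Day 84 through the end of study". The planned source is the diary: "Opioid consumption was to be recorded via subject diaries throughout the study". The concomitant-medication page is brought in because "Occasionally, a subject would report opioid consumption that was not recorded on the subject diary", and site staff then entered that intake on the page.

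For that page the SAP sets two conditions: the ATC level 3 text must be OPIOIDS, "and with a start date on or after the randomization date will be combined with records from the Opioid Products Administered CRF". The start-date condition is attached to concomitant-medication records. None is stated for the Opioid Products Administered CRF.

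Other sections bear on the rule:

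- SAP 9.2.2 (Medications): "Medications will with missing start dates will be considered ongoing on the first day of study drug administration", unless there is confirmation that the drug stopped earlier. A drug marked as continuing, or with an unknown stop date, is still concomitant.
- SAP 7.2.2: rescue may be oral or intravenous medication, or a higher pump speed.
- Protocol 5.5: route of administration is collected for prescription medications.
- SAP 9.5.2: the endpoint is analysed by ANCOVA at the two-sided 5% level. Appendix A gives it two tables (14.2.3.1.3 and 14.2.3.1.4).

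**The concern.** The endpoint is defined by when the opioid was consumed and by its route. The rule for the concomitant-medication page selects by when the record began and by drug class. These are different sets. A record can begin before randomization and cover intake after it, and an opioid can be in the right class without being oral.

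The page exists in this derivation to recover intake that the diary missed, so an omission there is not made good elsewhere. SAP 7.2.3 says diaries are as a rule not queried, and SAP Section 2 says the efficacy modules will receive no further cleaning. The derivation rule is therefore the remaining place to get the total right. At stake is the accuracy of a listed secondary endpoint that is compared between arms.

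**Working it through.** The documents give no sample size, effect size or expected total for this endpoint, so there is no figure to reproduce. The check sets the definition against the rule.

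**Step 1. Classify intake taken after randomization.**

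| Intake | Where recorded | Within the definition? | Counted by the rule? |
|---|---|---|---|
| Oral, any start date | Opioid Products Administered CRF | Yes | Yes |
| Oral, begun after randomization | Concomitant-medication page only | Yes | Yes |
| Oral, begun before randomization and continuing | Concomitant-medication page only | Yes | **No (0 mg)** |
| Oral, start date missing, continuing | Concomitant-medication page only | Yes | **No (0 mg)** |
| Intravenous, begun after randomization | Concomitant-medication page | No | **Yes** |

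In the fourth row, SAP 9.2.2 places the drug as ongoing at first study dose, which is before randomization. A date left blank does not satisfy the condition either.

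**Step 2. Can an earlier start date occur?** Yes, though the documents do not say how often.

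- SAP Section 4 and the protocol synopsis say that from Day 77 "subjects are permitted up to 60 mg-equivalent morphine per day only to manage possible withdrawal symptoms", one week before randomization on Day 84. Protocol 9.4 says subjects should be off oral opioid supplement on Days 77 to 83, and the schedule footnotes place the 60 mg allowance after Day 84. These passages must be reconciled.
- The stated criterion for randomization (Protocol 3.5.1.3, SAP Section 4) is a 5-day average VASPI of 50 mm or less. Being free of oral opioid is written beside it as something that should be so.
- Protocol 3.6.1 says that "if the medication is needed long term the medication should be recorded as a concomitant medication". This concerns medications in general and does not show that oral opioid supplement was logged this way.

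**Step 3. Size for one affected subject.** Assumptions: daily use throughout, morphine as the drug (so milligrams and morphine-equivalents coincide), and none of it in the diary. The doses are assumed, except that 60 mg/day is the stated maximum.

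Days = 119 − 84 = 35, or 36 if both end days count. Omitted amount = daily dose × days.

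- 15 mg/day: 15 × 35 = 525 mg (15 × 36 = 540 mg)
- 30 mg/day: 30 × 35 = 1,050 mg (30 × 36 = 1,080 mg)
- 60 mg/day: 60 × 35 = 2,100 mg (60 × 36 = 2,160 mg)

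If the diary missed only some days, the loss shrinks in proportion: 7 missed days at 30 mg/day is 7 × 30 = 210 mg.

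**Step 4. Direction.** The date condition can only lower a subject's total. The absent route condition can only raise it. The documents give no frequency for either, so the net effect on the arm difference cannot be signed.

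**The case against.** The strongest reply is that the gap is narrow. The diary is the planned source, its records enter without a start-date condition, and the other page holds intake missed only occasionally. Subjects should also be off oral opioid in the week before randomization. All of this stands: it limits how many records are affected, but it does not make the rule agree with the definition.

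A second reply is that the endpoint's first sentence and title already say oral. That is so. The fault is that the selection rule does not carry the limit out, although route is collected and could be used.

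Several stronger readings are tempting, and the documents do not support them:

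- *All ongoing oral opioid is lost.* Only use recorded solely on the concomitant-medication page is lost.
- *The arm difference is biased upward because control subjects rescue more.* The planning assumption is 55% failure against 20%, but nothing says rescue doses go on this page. Appendix A has a separate rescue listing (16.2.7.1). For subjects entering CNS-HYD202US, the failure visit is the last day of this trial, so intake after rescue lies at or beyond the window. The two errors also pull in opposite directions.
- *Patch opioids at rescue are counted.* Rescue is described only as oral or intravenous medication or a pump increase.
- *Intake is counted twice.* The page is described as holding what the diary lacked, so the sources are presented as complementary.
- *Primary failures under criterion 3a are missed.* SAP 7.1 and 9.5.1 do not say that the 7.2.3 data feed that criterion.

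A last reply is that a change now comes after unblinding and depends on uncleaned data. That also stands and shapes the fix.

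**Conclusion.** The point holds for the concomitant-medication part of the endpoint only. There, a stated rule contradicts the endpoint's own definition: it gives 0 mg to qualifying oral intake under an earlier or missing start date, and it would accept an intravenous opioid entered on the page. The second consequence is possible rather than shown.

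The per-subject loss could reach 1,050 mg at an assumed 30 mg/day, or 2,100 mg at 60 mg/day, over 35 days if the diary missed everything. The number of subjects and the net direction are unknown, and the overall effect may be small. This is a correction to one of several other secondary endpoints. The documents do not support extending it to the primary analysis.

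**What to change.** Amend the selection sentence in SAP 7.2.3 so that a concomitant-medication opioid record enters the total when:

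1. its route is oral;
2. its start is on or before the end of study, with a missing start date handled as in SAP 9.2.2 (Medications); and
3. its stop is on or after randomization, or it is ongoing.

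Count only the days from randomization to end of study, the period SAP 8.6 already uses for the randomized phase. Leave the handling of the Opioid Products Administered CRF as it is.

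The cost is one sentence and a small programming change on the locked data. The new rule needs stop dates and daily amounts, which come from data that will not be cleaned further. A record with an unknown stop date would run to the end of study and could overstate intake, so list the records whose inclusion changes. Because the study is already unblinded (SAP Section 2), label the change as made after unblinding and report the result under the rule as now written alongside it.
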